5.1 Investigational Product(s) / Intervention(s)

Placebo product: Toasted oat flour (Montana Gluten Free, Belgrade, Montana)

Active product: Partially defatted peanut flour (Golden Peanut Company, Alphretta, Georgia)

Refer to section 1.6, and applicable product labeling for known and potential risks to human participants associated with the investigational product(s) intervention(s).

5.2 Formulation, Packaging, Storage and Labeling

The drug is organic nonfat dry peanut. The drug will be purchased from the Golden Peanut Company, located in Alphretta, Georgia. The company states that the drug is manufactured under GMP for food products. No other nuts are processed at this facility. The peanut flour is not stored with material from other nuts. Analysis has been completed to determine the protein content in the bulk peanut powder. [name] will hold the IND.

The placebo will be toasted oat flour. The oat flour proposed for use in this study will be purchased in bulk from the Montana Gluten Free Processors, located in Belgrade, Montana. The company states that the drug is manufactured under GMP for food products. No other allergens such as peanuts, tree nuts, wheat, corn, and soy are processed at this facility.

5.3 Preparation, Administration, and Dosage

Each dose for daily at home immunotherapy will be provided to the participant in a single-dose lidded portion cup. The container will be a 2 oz Portion Cup PC-200 and XL250PC Portion Cup Lid (Fabri-Kal, Kalamazoo, MI), supplied by the MGH CRC. No other product will be present in the daily dosage. The doses will be refrigerated.

Drug product will be prepared (weighed, aliquoted into the single dose lidded portion cups, and placed in a transport bag) in the MGH CRC by trained Metabolic Kitchen Staff. Each visit the kitchen staff will calibrate the balance and then weigh and record weight of bulk peanut (or oat) flower in container. Next they will zero balance an empty vial, measure dose into empty vial, record weight, label vial, and then re-weigh bulk peanut (or oat) powder and container to ensure the correct amount of peanut (or oat) powder was removed. Participants will ingest daily dose of immunotherapy mixed with vehicle food which they will provide. The starting dose will be determined by the participant's threshold sensitivity during the modified rush phase of the protocol. After the initial dose has been determined the dose will follow the dosing schedule presented in Figure 15.3.

5.4 Accountability of Investigational Product(s) / Intervention(s)

Under Title 21 of the Code of Federal Regulations (21CFR §312.62) the investigator will maintain adequate records of the disposition of the investigational product(s) / intervention material(s), including the date and quantity of the drug received, to whom the drug was dispensed (participant-by-participant accounting), and a detailed accounting of any investigational product(s) / intervention material(s) accidentally or deliberately destroyed.

Records for receipt, storage, use, and disposition will be maintained by the study site. A dispensing log will be kept current for each participant. This log will contain the identification of each participant and the date and

quantity of investigational product(s) / intervention material(s) dispensed. Any drug that remains unused at the end of study will be destroyed.

All records regarding the disposition of the investigational product(s) / intervention material(s) will be available for inspection by the Clinical Research Associate (CRA) and NIAID.

5.5 Assessment of Compliance with Investigational Product(s) / Intervention Material(s)

Every study subject will be asked to record consumption of their home doses of peanut protein in a diary. In order to assess each subject's level of compliance with the investigational products, this diary will be reviewed for compliance during all study visits between DBPCFC1 and DBPCFC2 by the study staff. The proper method of recording and reporting accidental ingestions will also be reviewed with subjects following DBPCFC1. In order to be prepared for accidental ingestions or any possible adverse reactions to peanut protein doses, the proper method of carrying and using an epinephrine autoinjector will also be reviewed with the subjects throughout the study.

5.6 Modification or Discontinuation of Investigational Product(s) / Intervention Material(s)

5.6.1 Modification of Investigational Product(s) / Intervention(s)

Participants receiving active treatment who react to <1443 mg peanut protein during DBPCFC2 will be considered a treatment failure and be recommended to return to a strict peanut avoidance diet.

If the participant tolerates <4430 mg peanut protein during the DBPCFC3, he or she may elect to resume daily peanut protein dosing either at the highest tolerated dose during the challenge or 4000 mg peanut protein (whichever is less). If less than 4000 mg peanut protein, the daily dose will be increased by 25% every 2 weeks (\pm 4 days) as tolerated at the MGH CRC until they reach a dose of 4000 mg of peanut protein. They will continue on a dose of 4000 mg peanut protein for 1 year. At that time, they may elect to repeat a challenge.

At study end, those participants who are neither treatment failures nor achieve full tolerance, as determined by the DBPCFC3, may elect to have a nutrition consult to review a diet that would allow for the daily consumption of peanut protein at a dose that is tolerated without symptoms. The subject may also elect to resume strict avoidance. These subjects will continue to be followed at the MGH Food Allergy Center.

5.6.2 Premature Discontinuation of Investigational Product(s) / Intervention(s)

If the participant misses one or two days of the daily dose for any reason then he or she will continue on the same dose. If the participant misses the dose for three days, the participant will be asked to return to the MGH CRC for the next daily dose to ensure that there are no adverse effects from resuming dosing. If the participant misses their dose for four or more days, he/she will have to return to the MGH CRC for a modified rush protocol to escalate back to the highest previously tolerated dose beginning at 50%. Participants will be terminated from the study (section 4.3) if dose adjustment is required more than twice for missed at-home dosing.

6 OTHER MEDICATIONS

6.1 Concomitant Medications

Concomitant medications may be used as follows: Other medications may be used during study participation unless noted in section 6.4.

6.2 Prophylactic Medications

NA

6.3 Rescue Medications

The following rescue medications may be used if a subject experiences an adverse event:

- Albuterol
- Epinephrine
- Diphenhydramine
- Hydroxyzine
- Ranitidine
- Corticosteroid

6.4 Prohibited Medications

Use within the past year of other systemic immunomodulatory treatment. including allergen immunotherapy, use of biologics with an immune target, including Xolair is prohibited.

Prior to the food challenges, patients will be asked to restrict the use of antihistamines (short-acting, 72 hours: long-acting, 7 days), beta-agonists (12 hours), theophylline (12 hours), and cromolyn (12 hours). For visits that include skin prick testing, patients will be asked to restrict the use of antihistamines (short-acting, 72 hours: long-acting, 7 days).

7 STUDY VISITS AND PROCEDURES

Appendix 16.1 summarizes the schedule of events for the study.

7.1 Enrollment and Randomization

Participants will be recruited from oral immunotherapy-interested individuals who have contacted us in response to announcements and advertisements, referrals from Allergy/ Immunology Clinics, and by identification using the Partners Research Participant Data Registry. The referring physician may send potential participants and/or their

23 of 68

parents a recruitment letter. The letter will include contact information for study staff so the participant and/or their parents can opt-in to participate. This research study will be explained in lay terms to each potential research participant. The potential participant or participant's legal guardian will sign an informed consent form before undergoing any baseline study procedures. Participants age 14-17 will co-sign the consent form with their legal guardian. Participants age 7-13 will sign a child-specific assent form and their legal guardian will sign the consent form.

Participants enrolled as minors will be provided an adult consent form for signature when they reach age 18 and will be re-consented before any study procedures take place. Any "new adult" who refuses consent will be removed from the study. Participants who are deemed eligible for the study (see section 4) will be enrolled and assigned a unique participant number.

Following DBPCFC1, participants will be randomly assigned by the study statistician to treatment or placebo groups at a ratio of 3:1. Following DBPCFC2, assignment will be unblinded and placebo participants will be offered open-label active treatment following the same desensitization procedures (Modified Rush, Build Up and Maintenance).

7.2 Screening Visit (Day -30 to -7)

Informed consent will be obtained at this visit as described above. The screening visit will involve a medical history, physical examination, standard skin prick testing (SPT), and a blood draw (10 ml). The physical examination will include pulmonary function testing. Serum will be collected for total and peanut-specific IgE antibody measurements and stored for specific IgG4 if subject is eligible. The blood draw will be performed if relevant testing has not been performed within 2 months of the screening visit. If relevant testing has been performed with 2 months of the screening visit, a copy of the results will be obtained. Urine will be collected for a Human Chorionic Gonadotropin (HCG) test to determine pregnancy in female participants of childbearing potential. Women of childbearing age will be advised on birth control options for the duration of this study. If a participant is found to be pregnant at any time during this study, she will be immediately removed. The study physician will confirm eligibility by history, SPT and specific IgE following this visit.

7.3 Baseline Visit (Day 0)

The baseline visit will involve a medical history, physical examination, and a blood draw for mechanistic studies. The physical examination will include pulmonary function testing and endpoint titration SPT. Urine will be collected for a Human Chorionic Gonadotropin (HCG) test to check for pregnancy in female participants of childbearing potential.

The participants and/or their parents will be instructed on recording adverse events and any known accidental ingestion that occurs during the study. The participant and his or her parents will also have a nutritional consultation with a registered dietitian to enhance adherence to a peanut-free diet. Participants will be asked about their preferred and tolerated vehicle food to be used during the Build Up and Maintenance visits for the duration of the study.

7.4 Main Study Visits

7.4.1 Double-Blind Placebo-Controlled Food Challenge 1 (Day 28)

Participants will come to the MGH CRC four weeks (± 4 days) after the baseline visit for a double-blind, placebo -controlled food challenge (DBPCFC1) to peanut. In a DBPCFC, two challenges, one containing placebo material (toasted oat flour) and one containing peanut flour will be performed on two days within a two week period. The order of challenge will be determined by coin toss by the dietitian and will be unknown to the study nurse, investigator, and study participant. The MGH CRC dietician will prepare the challenge materials. Details of the DBPCFC procedure are below in section 7.7.1.

Prior to each challenge, the participant will have a physical exam with vital signs, spirometry, and an IV will be placed. A negative urine pregnancy test will be documented for female participants of child-bearing potential; if the test is positive, the visit will be cancelled and if pregnancy is confirmed, the subject will be withdrawn from the study. The participant will be required to have a baseline FVC and FEV1 >80% of their predicted values and an FEV1/FVC of >0.7 or the DBPCFC will be rescheduled. A study nurse who is blinded to the testing material will administer the challenge. The supervising physician will be present during the challenge and will also be blinded to testing material.

A member of the study staff will follow up with participant with a telephone call the day after the DBPCFC for active safety monitoring.

If the participant reacts at the 300 mg dose of peanut protein or less (443 mg cumulative), he/she will be randomized to receive active or placebo OIT.

7.4.2 Modified Rush Visit (Day 42)

Two weeks following the completion of DBPCFC1, the participant will come to the MGH CRC for the modified rush procedure as shown in Figure 15.2. The participant will undergo a medical history and physical exam including vital signs, and spirometry. An IV will be placed. A negative urine pregnancy test will be documented for female participants of child-bearing potential; if the test is positive, the visit will be cancelled and if pregnancy is confirmed, the subject will be withdrawn from the study. The participant will be required to have a baseline FVC and FEV1 >80% of their predicted values and an FEV1/FVC of >0.7 or the visit will be rescheduled. A study nurse who is blinded to the treatment material will administer the doses. The supervising physician will be present during the procedure and will also be blinded to testing material. This visit will occur 2 weeks after the completion of DCPCFC1.

7.4.3 Build Up Visits (Days 43–350)

Beginning with the day after the Modified Rush Visit and every two weeks following that, the participant will come to the MGH CRC for a Build Up Visit during which an increased dose of study product is administered. Subjects will advance sequentially through an up-dosing schedule as described in section 7.7.2.2. The dosing escalation will be incremental based on previous OIT studies [?]. When the participant reaches the 4000 mg peanut protein dose they will enter the maintenance phase. The participant will undergo a medical history and physical exam including vital signs, and spirometry. The symptom diary (Appendix 16.2) will be reviewed for evidence of symptoms associated with the previous interval dose. A negative urine pregnancy test will be documented for female participants of child-bearing potential; if the test is positive, the visit will be cancelled and if pregnancy is confirmed, the subject will be withdrawn from the study. The participant will be required to have a baseline FVC

and FEV1 >80% of their predicted values and an FEV1/FVC of >0.7 or the visit will be rescheduled. A study nurse who is blinded to the treatment material will administer the doses.

7.4.4 Maintenance Visits (Days 350-434)

Maintenance visits will occur on the MGH CRC monthly during the 12 weeks of maintenance therapy. Each visit will involve a medical history and physical examination. The medical history will consist of a structured interval clinical history and review of systems concerning any types of allergic symptoms related to their food allergy, atopic dermatitis or asthma. The participants and/or their parents will record any known accidental ingestion that occurs during the study. The physical exam will include vital signs, and spirometry. A negative urine pregnancy test will be documented for female participants of child-bearing potential; if the test is positive, the visit will be cancelled and if pregnancy is confirmed, the subject will be withdrawn from the study.

Blood will be collected and skin prick testing will be performed at three follow-up visits for research laboratory studies at baseline, on maintenance therapy (after 12 weeks at 4000 mg of peanut protein or maximum tolerated) prior to DBPCFC2, and prior to DBPCFC3 (12 weeks post avoidance). An additional blood draw will occur during build up (12 weeks after beginning treatment). Blood will be drawn by trained study staff or Clinical Research nurses. Urine will be collected from female participants for a Human Chorionic Gonadotropin (HCG)-based pregnancy test at all follow up visits throughout the study.

7.4.5 Double-Blind Placebo-Controlled Food Challenge 2 (Day 434)

After taking maintenance dose for 12 weeks, participants will come to MGH CRC for their second double-blind, placebo-controlled food challenge (DBPCFC2).

7.4.6 Avoidance Visit (Day 434–518)

An avoidance study visit will occur on the MGH CRC four weeks (+/- 4 days) before the Double-Blind Placebo-Controlled Food Challenge 3. This visit will involve a medical history and physical examination. The medical history will consist of a structured interval clinical history and review of systems concerning any types of allergic symptoms related to their food allergy, atopic dermatitis or asthma. The participants and/or their parents will record any known accidental ingestion that occurs during the study. The physical exam will include vital signs, and spirometry. A negative urine pregnancy test will be documented for female participants of child-bearing potential; if the test is positive, the visit will be cancelled and if pregnancy is confirmed, the subject will be withdrawn from the study. This visit will include a blood collection for mechanistic studies.

7.4.7 Double-Blind Placebo-Controlled Food Challenge 3 (Day 518)

After 12 weeks of complete peanut avoidance after the DBPCFC2, participants will come to MGH CRC for their third double-blind, placebo-controlled food challenge (DBPCFC3). The DBPCFC3 will be similar to DBPCFC2, differing only in the dosing schedule. See Section 7.7.1 for details.

7.5 Open Label Treatment

Participants receiving placebo treatment will be offered open-label active treatment after DBPCFC2. The open-label oral immunotherapy schedule will follow a seperate protocol for participants initially receiving placebo treatment.

Participants receiving active treatment who fail the post-avoidance challenge will be offered the option to repeat the desensitization up to the level reached during initial up dosing. Participants will then be referred to the MGH Food Allergy Center or other qualified allergist to be advised on diet choices and appropriate peanut protein exposure.

Following active therapy, participants will be referred to the MGH Food Allergy Center or other qualified allergist.

7.6 Visit Windows

Study visits should take place within the time limits below:

• Subjects will have a ± 14 day window to complete study visits.

7.7 Study Procedures

7.7.1 Double-Blind Placebo-Controlled Food Challenge

In a DBPCFC, two challenges, one containing placebo oat flour and one containing peanut flour, will be performed. The dietitian will perform the preparation of the challenge materials. Prior to the food challenge, participants will be asked to restrict the use of antihistamines (short-acting, 72 hours: long-acting, 7 days), beta-agonists (12 hours), theophylline (12 hours), and cromolyn (12 hours). For DBPCFC1, one challenge will consist of 5 doses of peanut powder given every 20 minutes in increasing amounts up to a cumulative total of 443 mg of peanut protein masked by inclusion in vehicle food. Available vehicle foods will include rice milk, soymilk, mint chocolate mousse, or applesauce. The other challenge will consist of oat flour given also in 5 doses in an identical volume of vehicle food. For the active challenge, the first ingested dose will be 3 mg, then increasing to 10 mg, 30 mg, 100 mg, and 300 mg of peanut protein[?]. The placebo challenge doses will be the equivalent amount of oat flour by weight.

The protocol of the DBPCFC2 will be identical to DBPCFC1, but with additional doses of 1000 mg and 3000 mg for a cumulative dose of 4443 mg peanut protein. DBPCFC3 will follow a slightly different schedule of doses: 30 mg, 100 mg, 300 mg, 1000 mg, and 3000 mg for a cumulative dose of 4430 mg peanut protein.

If the participant has a subjective reaction to one of the doses, the study nurse may repeat that dose or consult with the supervising physician. If symptoms do not recur, the study nurse will continue the DBPCFC protocol after confirming with the supervising physician. If the study nurse is unsure about how to proceed, the supervising physician will be consulted to determine the appropriate action. Food challenges will be immediately stopped and the participant promptly treated for objective signs and symptoms as indicated in Figure 15.4, consistent with the 2010 NIAID-sponsored expert guidelines for the diagnosis and management of food allergies [?].

After the final dose of each challenge or the resolution of any suspected reaction symptoms, the participant will be observed for a minimum of 2 additional hours.

All food challenges will be performed under direct physician supervision. The supervising physician may stop a challenge if he/she feels it is in the best interest of the participant. Incomplete or indeterminate challenges will be rescheduled.

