1.6 Risks

1.6.1 Risks of Investigational Product(s) / Intervention(s)

In previous studies of peanut oral immunotherapy, mild to moderate side effects of dose increases (done at study visits) have included: lung symptoms (e.g., cough, increased use of albuterol for individuals with asthma), GI tract symptoms (nausea, vomiting, diarrhea), skin symptoms (hives, itchiness) and nose symptoms (e.g. stuffiness) More rarely, similar side effects have also occurred during doses taken at home, especially when the child had an intercurrent illness (e.g., a cold), exposure to another allergen (e.g., during pollen season for those who have seasonal allergies), in association with exercise or when taken on an empty stomach [? ?]. Menses together with exercise has also been reported in one case as a potential co-factor for reactions to OIT [?]. Additional rare risks of OIT and food challenges are those of anaphylaxis and include respiratory obstruction (e.g., wheezing, coughing, and swelling of the voice box) and cardiovascular problems such as a drop in blood pressure or cardiovascular collapse. Most OIT studies to date have targeted a younger patient population. A 2011 study [?] of children aged 3 to 18 noted that peanut allergic patients over 10 years of age reacted at lower eliciting doses than those in the youngest tertile (< 5.5 years). They did not attempt to report on reaction severity. The median eliciting dose for the oldest age group was approximately 45 mg of peanut protein with an interquartile range of 4.5 to 200 mg peanut protein. In a study of the efficacy of anti-lgE for the treatment of adolescents and adults (13-59 years) with peanut allergy, the mean pre-treatment eliciting dose was 330 mg of peanut flour (range 1 - 2000 mg) [?].

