2.2 Secondary Objective(s)

2.2.1 Clinical:

- To evaluate whether PN OIT induces increased tolerance, defined as a statistically significant increase in the median eliciting dose (ED) from DBPCFC1 to DBPCFC3.
- To evaluate whether PN OIT induces clinical desensitization, defined as 1) a median 10-fold or greater increase in ED from DBPCFC1 to DBPCFC2; 2) a statistically significant higher median ED at DBPCFC2 between active and control treatment; and 3) a significantly lower frequency of accidental ingestion reactions in active versus control treatment.
- To evaluate the safety of PN OIT.

2.2.2 Mechanistic:

- To determine whether PN OIT induces a statistically significant increase in the TCR clonal diversity of Treg
 populations during active treatment among participants who achieve increased clinical tolerance (Tolerance
 and Partial Tolerance Groups as defined in clinical endpoints) versus the Treatment Failure Group.
- To determine whether PN OIT suppresses mast cells by inducing a significant suppression of the median ED on end-point dilution skin testing in actively treated participants by the end of maintenance therapy.
- To determine whether PN OIT suppresses basophils as defined by a 10-fold suppression of peanut-specific basophil ED in actively treated participants by end of maintenance.
- To determine whether either mast cell or basophil suppression at the end of maintenance therapy is significantly associated with clinical outcomes following avoidance.

2.2.3 Exploratory:

- To describe the gene expression profiles and clonal diversity of regulatory and effector T cell subsets before
 and after OIT to better understand the phenotype and ontogeny of these subsets and potentially discover
 new therapeutic pathways.
- To engineer human MHC class II tetramers on common HLA backgrounds and map T cell epitopes of the dominant peanut allergens for use in validating earlier findings and for future studies of peanut-specific immune responses in humans.
- To determine whether microbial dysbiosis is associated with the development of desensitization, oral tolerance, or persistent gastrointestinal adverse events while on oral immunotherapy.

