3.1.2 Secondary Endpoint(s)

Secondary endpoints are:

Clinical:

- Tolerance:
 - The change in median eliciting dose (ED) from DBPCFC1 to DBPCFC3.
- Desensitization:
 - The change in median eliciting dose (ED) from DBPCFC1 to DBPCFC2.
 - The frequency of accidental ingestion reactions in active versus control treatment.
- Safety:
 - Anaphylaxis requiring more than 1 administration of epinephrine; or hospitalization.
 - Death as a result of the investigational product.
 - The rate of reported adverse advents due to accidental ingestions in the active versus placebo groups.

Mechanistic:

- The change in the TCR clonal diversity of in vitro allergen-expanded Treg cells and induced Treg cells measured by TCRβ CDR3 sequence clonotyping of sorted cells during active treatment among participants who achieve increased clinical tolerance (Tolerance and Partial Tolerance Groups as defined in clinical endpoints) versus the Treatment Failure Group.
- The change in ED of end-point dilution skin testing between actively treated and placebo treated participants following maintenance therapy.
- The change in ED of end-point dilution skin testing among actively treated participants following maintenance therapy and avoidance between clinical outcome groups.

- The change in peanut-specific basophil ED in actively treated participants at the end of maintenance and the end of avoidance between clinical outcome groups.
- The change in peanut allergen-specific IgG4 in actively treated participants by the end of maintenance between clinical outcome groups.
- The change in Ara h 2 specific surface and secreting B cells between baseline (measured after 12 weeks
 of treatment) and the end of maintenance.
- Statistically significant gene expression changes by transcriptional profiling of regulatory and effector T cell participants before and after OIT between clinical outcome groups.

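### DBPCFC3 cannot record an eliciting dose below 30 mg but DBPCFC1 starts at 3 mg, so the secondary DBPCFC1-to-DBPCFC3 ED change can be inflated for the most sensitive participants

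*Combined protocol and SAP*

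**What the plan says.** Section 7.7.1 sets the dose steps. At DBPCFC1, "the first ingested dose will be 3 mg, then increasing to 10 mg, 30 mg, 100 mg, and 300 mg of peanut protein". DBPCFC2 adds 1000 mg and 3000 mg. For the last challenge, "DBPCFC3 will follow a slightly different schedule of doses: 30 mg, 100 mg, 300 mg, 1000 mg, and 3000 mg". The section puts the total of that last schedule at 4430 mg.

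Section 3.1.2 lists under its tolerance heading "The change in median eliciting dose (ED) from DBPCFC1 to DBPCFC3". Section 2.2.1 gives the success criterion: increased tolerance is "defined as a statistically significant increase in the median eliciting dose (ED) from DBPCFC1 to DBPCFC3". It sets no minimum fold change; the 10-fold requirement in that section belongs to the DBPCFC1-to-DBPCFC2 comparison.

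Section 9 names no test for ED. It does not say whether ED means the single provoking dose or the cumulative dose, although the numerical cut-offs elsewhere (443, 430, 1443, 4430 mg) are cumulative totals. It has no rule for a reaction at the first DBPCFC3 dose.

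Under Sections 7.1 and 7.5, assignment is unblinded after DBPCFC2 and placebo participants are offered open-label treatment, so no concurrent control at DBPCFC3 is assured.

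**The concern.** The lowest ED that can be recorded is 3 mg at one end of the comparison and 30 mg at the other. Someone whose sensitivity is exactly what it was at entry, but whose threshold lies below 30 mg, must show a rise. Because the objective is met by any significant increase and there is no assured placebo comparison to cancel the effect, part of an observed rise could come from the dose schedule.

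Full return to baseline is a relevant null here. Participants reach DBPCFC3 as desensitised only after an ED of at least 1443 mg at DBPCFC2, and Section 9.1 expects 14 of the 22 who go on to avoidance to lose tolerance. Section 1.2 gives separating lasting tolerance from desensitisation as the purpose of the avoidance challenge.

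**Working it through.** **1. The plan's totals reproduce.** DBPCFC1: 3+10+30+100+300 = 443 mg. DBPCFC3: 30+100+300+1000+3000 = 4430 mg.

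**2. What an unchanged participant records** (same single dose provokes at both challenges):

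| Step at DBPCFC1, single (cumulative) | Step at DBPCFC3, single (cumulative) | Ratio, single | Ratio, cumulative |
|---|---|---|---|
| 3 (3) | 30 (30) | 10 | 30/3 = 10 |
| 10 (13) | 30 (30) | 3 | 30/13 = 2.3 |
| 30 (43) | 30 (30) | 1 | 30/43 = 0.70 |
| 100 (143) | 100 (130) | 1 | 130/143 = 0.91 |
| 300 (443) | 300 (430) | 1 | 430/443 = 0.97 |

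The bottom two steps rise. On the cumulative scale the other three fall slightly.

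**3. Outcome categories.** Partial Tolerance needs at least 430 mg and more than 10-fold; Tolerance needs 4430 mg without symptoms. None of the five unchanged rows qualifies. The floor value of 30 mg is below 430 mg, and is exactly 10-fold over 3 mg, not more.

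**4. How many participants are affected.** The trial's own ED distribution is not given. Section 1.6.1 cites, for the oldest group of a study in ages 3 to 18, "approximately 45 mg of peanut protein with an interquartile range of 4.5 to 200 mg peanut protein". Taking that as an assumption (log-normal on each side of the median, cut at the entry limit), about 42% have a baseline ED at the 3 mg or 10 mg step.

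The modified rush visit reduces this share. Section 7.7.2.1 requires 1.5 mg to be tolerated to stay in the study; the table in Section 15.2 marks 3.0 mg as the minimum. These two passages must be reconciled. By that table, cumulative intake is 3.0 mg at the 1.5 mg step and 6.0 mg at the 3.0 mg step. If a fixed cumulative threshold governs reactions, everyone with a baseline ED of 3 mg therefore leaves before build-up. Applying either limit brings the share to about 14-27%.

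**5. Effect on a test.** Simulated trials of 22 participants with no true change, within-person SD 0 to 0.5 log10:

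| Test and scoring | Rush limit | Falsely shows an increase |
|---|---|---|
| Paired signed-rank, cumulative | ignored | 56-75% |
| Paired signed-rank, cumulative | 1.5 mg | 6-34% |
| Paired signed-rank, cumulative | 3.0 mg | 1-25% |
| Paired signed-rank, single dose, no common floor | ignored | 88-99% |
| Paired signed-rank, single dose, no common floor | applied | 54-91% |
| Unpaired rank-sum, cumulative | ignored | 4-14% |
| Paired signed-rank, single dose, common ≤30 mg floor | ignored | 6-18% (0-14% in a second run) |

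The nominal rate in this direction is 2.5% for a two-sided 5% test. With other assumed tails, and with either single or cumulative dose driving reactions, the first row becomes 33-66%.

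**6. A check without the borrowed distribution.** On single-dose scoring with no within-person noise, nobody falls, so an exact two-sided sign test rejects once 6 of 22 rise (2 × 0.5^6 = 0.031; five rises give 2 × 0.5^5 = 0.0625). The chance of at least 6 rises is 2%, 27%, 69% and 93% if 10%, 20%, 30% and 40% have a baseline ED below 30 mg.

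**7. Group medians.** Without the rush limit, the no-change population median goes from 43 to 30 mg (cumulative) or 30 to 30 mg (single dose). With it, the cumulative median goes from 143 to 130 mg. Under the planned 8 versus 14 split, the median of 22 lies between the 11th and 12th values. The floor then matters only if at least 11 of the 14 failures have a true ED below 30 mg: probability 0.4% if 40% of them do, 2.9% if 50% do.

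**The case against.** The strongest reply is that the modified rush limit removes most of the people on whom the artefact depends. On cumulative scoring it takes the false-increase rate from 56-75% to 1-34%, which overlaps the 6-18% that remains on a common grid. This stands, with two limits. The rush visit allows longer intervals, repeated doses and investigator judgement, so it may not filter cleanly. And if single dose rather than cumulative dose provokes, a participant with a threshold between 1.5 and 3 mg passes the 1.5 mg limit.

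Second, the endpoint is worded as a change in the median and the plan names no paired test. The group median does not rise under no change at population level, and a rank-sum test on cumulative ED gives only 4-14%. This also stands. It shows that the bias depends on an analysis choice the plan leaves open. The median of a sample of 22 can still move upward by chance, in about 33-60% of the simulated no-change trials without the rush limit.

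Third, the baseline distribution is borrowed. The same section cites a study in ages 13 to 59 with a mean pre-treatment ED of 330 mg of peanut flour (range 1 to 2000 mg), but gives no quartiles and counts flour, not protein. The share below 30 mg is therefore unknown.

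A reader might infer that the Tolerance and Partial Tolerance categories, and so the primary Treg comparison and its power, are inflated. The documents do not support that: those categories start at 430 mg.

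**Conclusion.** The floor is real and is fixed by the dose schedules. An unchanged participant with a baseline ED at either of the two lowest steps records a false rise of 10-fold, or of 2.3-fold (cumulative) or 3-fold (single dose). Only the secondary DBPCFC1-to-DBPCFC3 ED change is exposed.

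Whether this produces a false positive result depends on the share with a baseline ED below 30 mg, the ED scale and the test; the documents fix none of these. The simulated rates run from 1% to 99% across those choices, so they support specifying the analysis, not predicting an outcome. They assume that all 22 return to baseline, whereas the plan expects 8 of the 22 to be at least partially tolerant. It would therefore be wrong to read 56-75% as the chance that this trial falsely declares tolerance. This is a cheap improvement to one secondary endpoint.

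**What to change.** For this endpoint only, state in Section 9 that:

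- ED at DBPCFC1 and DBPCFC3 is scored on the shared single-dose steps: ≤30, 100, 300, 1000, 3000 mg, no reaction;
- any reaction at or below the 30 mg dose is coded ≤30 mg at both challenges, so that a pair in that range is a tie;
- the change is tested with a paired signed-rank test.

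If the same single dose provokes, every unchanged row in the table of step 2 then has a ratio of 1. Keep the cumulative cut-offs for eligibility and the outcome categories. No challenge dose, visit or sample size changes.

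Costs: true improvement within the ≤30 mg range is not counted, and the document carries a second ED scale, which must be labelled. If the change is judged a principal feature, Section 9.4 requires an amendment.

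The fix removes the floor artefact, not all bias. If cumulative dose drives reactions, an unchanged threshold of 40 mg is reached at the 30 mg step of DBPCFC1 (cumulative 43) but only at the 100 mg step of DBPCFC3 (cumulative 130), a one-step rise. The same happens for thresholds of 130-143 mg and 430-443 mg. Large within-person variability also leaves some excess. Where cumulative scoring is used and the rush limit filters well, the gain is therefore small; the fix matters most if single-dose scoring is intended or the limit leaks.
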